### 8.3.3

## Secondary Analysis (or Analysis of Secondary Endpoints)

### Definition and analytical plan for secondary efficacy endpoints:

**(a) Duration of response (DR):** The DR for CR and PR will be measured from the date that the best response is first recorded until the date that PD is documented over the period of 1 year. For patients who continue treatment post progression, the date of PD documentation will be used for analysis. The DR will be summarized using descriptive statistics (N, mean, standard deviation, minimum, and maximum).

**(b) Disease control rate (DCR):** DCR will be defined as the percentage of patients who have achieved CR, PR, or SD for at least 12 weeks. The DCR will be summarized using descriptive statistics (N, mean, standard deviation, minimum, and maximum).

**(c) Progression-free Survival (PFS):** PFS will be calculated as 1+ the number of days from the first dose of study drugs to documented radiographic progression or death due to any cause over a period of 1 year. For patients who continue treatment post-progression, the date of radiographic progression will be used for PFS analysis. The Kaplan-Meier analysis will be used to calculate the median PFS with 95% confidence interval.

**(d) Overall Survival (OS):** OS will be calculated as 1+ the number of days from the first dose of study drugs to death due to any cause over a period of 1 year. The Kaplan-Meier analysis will be used to calculate the median OS with 95% confidence interval.

**(3) Definition and analytical plan for safety and tolerability endpoints:** The safety population will consist of all subjects who receive any amount of study treatment. Safety will be assessed by evaluation of AEs. All safety analyses will be performed using the safety population. Adverse event terms recorded on the CRFs will be mapped to preferred terms using the Medical Dictionary for Regulatory Activities (MedDRA). Seriousness, severity grade and relationship to study treatment will be assessed by the investigator. Severity grade will be defined by the National Cancer Institute (NCI) CTCAE v4.03. Listings of AEs will be provided.

Separate tables will present the following by dose group and study phase:

- All treatment-emergent AEs
- Treatment-emergent AEs by CTCAE grade
- Grade 3 or greater treatment-emergent AEs
- Treatment-related, treatment-emergent AEs
- Dose-limiting toxicity AEs
- Serious treatment-emergent AEs
- Treatment-emergent AEs with an outcome of death
- Treatment-emergent AEs leading to discontinuation of trametinib.
- Treatment-emergent AEs resulting in interruption or reduction or delay of trametinib.

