| 
Efficacy Assessments
 | 
Efficacy measures will include tumor assessments by CT scans of the chest, abdomen, and pelvis with appropriate slice thickness per RECIST Version 1.1. Brain imaging (CT/MRI) is required at baseline and follow-up scans should include the brain in patients with baseline brain lesions. All sites of disease should be followed and the same imaging methodology should be used throughout the study. Tumor assessments will be carried out at screening and every 8 weeks <math>\pm</math> 1 week from the time of trametinib initiation and thereafter until tumor progression. Patients are required to have an end-of-treatment tumor scan using the same methodology used at screening unless:
 
 
• The patient has radiographic evidence of disease progression while on study, or
 
• It has been < 2 weeks since their last on-study scan
 
 
Patients who discontinue trametinib without progression should continue to be scanned per standard of care until disease progression occurs.
 |

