### 2.4.2 Secondary Endpoints

- Efficacy: DR, DCR, PFS, and OS according to RECIST Version 1.1 criteria as determined by investigator assessment.
  - The DR for CR and PR will be measured from the date that the best response is first recorded until the date that PD is documented. For patients who continue treatment post progression, the date of PD documentation will be used for analysis.
  - DCR will be defined as the percentage of patients who have achieved CR, PR, or SD for at least 12 weeks.
  - PFS will be calculated as 1+ the number of days from the first dose of study drugs to documented radiographic progression or death due to any cause over a period of 1 year. For patients who continue treatment post-progression, the date of radiographic progression will be used for PFS analysis.
  - OS will be calculated as 1+ the number of days from the first dose of study drugs to death due to any cause over a period of 1 year.
- Safety and tolerability:
  - All treatment-emergent AEs
  - Treatment-emergent AEs by CTCAE grade
  - Grade 3 or greater treatment-emergent AEs
  - Treatment-related, treatment-emergent AEs
  - Dose-limiting toxicity AEs
  - Serious treatment-emergent AEs
  - Treatment-emergent AEs with an outcome of death
  - Treatment-emergent AEs leading to discontinuation of trametinib.
  - Treatment-emergent AEs resulting in interruption or reduction or delay of trametinib.

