**Duration of Response**

**Duration of overall response**

The duration of overall response is measured from the time measurement criteria are met for CR or PR (whichever is first recorded) until the first date that recurrent or progressive disease is objectively documented (taking as reference for progressive disease the smallest measurements recorded since the treatment started).

The duration of overall CR is measured from the time measurement criteria are first met for CR until the first date that recurrent disease is objectively documented.

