### Progression-Free Survival

Progression-free survival (PFS) is defined as the duration of time from start of treatment to time of progression.

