### 8.2 Determination of Sample Size and Accrual Rate

#### 8.2.1 Sample Size and Power Estimate

The primary endpoint is objective response rate (ORR). To provide 80% power to detect a 30% ORR compared to the null hypothesis of a 10% ORR in each cohort, 27 patients will be enrolled, with the goal of obtaining 24 evaluable patients. Using a Simon 2-stage design, if we do not observe at least 2 responses within the first 15 patients, enrollment will be stopped due to lack of efficacy.

The primary efficacy analysis will be based on one-sided exact binomial test comparison of the observed ORR in patients receiving at least one dose of study treatment to the null-hypothesized value of 10%, using the 5% significance level. Secondary time-to-event endpoints (DR, PFS and OS) will be summarized using Kaplan-Meier estimates with associated 95% confidence limits. The secondary DCR endpoint will be summarized as a proportion with an exact binomial 95% confidence interval. Safety analyses will be descriptive summaries of AEs by patient and type.

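### Duration of response ends only at documented progression, never at death; the planned Kaplan-Meier analysis would then be biased upward, and the alternative descriptive summary leaves such patients undefined

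*Combined protocol and SAP*

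**What the plan says.** DR is defined three times.

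- Section 2.4.2, where the clock stops once PD has been established: "The DR for CR and PR will be measured from the date that the best response is first recorded until the date that PD is" (final word of the sentence omitted here).
- Section 7.1.1.3, Duration of overall response: from the first CR or PR "until the first date that recurrent or progressive disease is objectively documented".
- Section 8.3.3(a): "measured from the date that the best response is first recorded until the date that PD is documented over the period of 1 year".

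None of these names death, and no section gives a censoring rule for DR.

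Two analyses of DR are planned. Section 8.2.1 states: "Secondary time-to-event endpoints (DR, PFS and OS) will be summarized using Kaplan-Meier estimates with associated 95% confidence limits". Section 8.3.3(a) states: "The DR will be summarized using descriptive statistics (N, mean, standard deviation, minimum, and maximum").

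PFS is defined in two ways. Sections 2.4.2 and 8.3.3(c) end it at "documented radiographic progression or death due to any cause over a period of 1 year". Section 7.1.1.3 leaves death out: "Progression-free survival (PFS) is defined as the duration of time from start of treatment to time of progression".

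On imaging, the Abstract states: "Tumor assessments will be carried out at screening and every 8 weeks", with a one-week window. After treatment, section 6.1.4 sets visits every 3 months.

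**The concern.** A responder can die before a scan shows progression. Scans are 8 weeks apart on treatment and visits are 3 months apart afterwards. The side-effect list in section 4.1.1 includes fatal intracranial hemorrhage, cardiac failure, pneumonitis and interstitial lung disease.

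For such a patient the response has ended, but the DR definition records no end. If DR is analysed by Kaplan-Meier with progression as the only event, the patient leaves the risk set as a censored observation. The estimator then assumes that this patient has the same future chance of progressing as those still at risk. Death rules that out: it is a competing event, and censoring it keeps the curve too high.

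The same death is a PFS event under 2.4.2 and 8.3.3(c). The two endpoints would then treat one patient differently. In a single-arm trial with few responders, DR is what tells the reader whether the responses last, so its definition should be unambiguous.

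**Working it through.** **No stated figure to reproduce.** The documents give no expected DR, no event count and no death rate among responders. The defect is shown by comparing the definitions; its size can only be illustrated.

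**Step 1. How a responder who dies without documented progression is handled**

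| Section | Endpoint and method | Result |
|---|---|---|
| 2.4.2, 7.1.1.3, 8.3.3(a) with 8.2.1 | DR, Kaplan-Meier | Not an event; in practice censored |
| 8.3.3(a) | DR, mean and SD | No end date; handling not stated |
| 2.4.2, 8.3.3(c) | PFS | Event |
| 7.1.1.3 | PFS | Not an event |

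**Step 2. Number of responders.** Section 8.2.1 gives 27 enrolled and response rates of 10% (null) and 30% (target). 0.10 × 27 = 2.7 and 0.30 × 27 = 8.1, so about 3 to 8.

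**Step 3. Effect on the Kaplan-Meier median.** Assume constant hazards, and let a share f of response-ending events be deaths without documented progression. If the total hazard is λ, the true median is m = ln 2/λ. With deaths censored, the estimated hazard is (1 − f)λ and the median reads m/(1 − f). The relative overstatement, 1/(1 − f) − 1, does not depend on m. For an assumed m of 6 months:

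| f (assumed) | Median with deaths censored | Overstatement |
|---|---|---|
| 5% | 6/0.95 = 6.3 | 5% |
| 10% | 6/0.90 = 6.7 | 11% |
| 20% | 6/0.80 = 7.5 | 25% |
| 30% | 6/0.70 = 8.6 | 43% |

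**Step 4. One death in a small group.** Suppose the death is the first DR event among n responders. When k responders remain in response, the curve reads k/(n − 1) if the death is censored and k/n if it is an event. Binomial SE = √(e(1 − e)/n), with e = k/n.

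| n | Later progressions | Censored | Event | Gap | SE |
|---|---|---|---|---|---|
| 8 | 1 | 6/7 = 0.857 | 6/8 = 0.750 | 0.107 | 0.153 |
| 8 | 2 | 5/7 = 0.714 | 5/8 = 0.625 | 0.089 | 0.171 |
| 8 | 3 | 4/7 = 0.571 | 4/8 = 0.500 | 0.071 | 0.177 |
| 6 | 1 | 4/5 = 0.800 | 4/6 = 0.667 | 0.133 | 0.192 |
| 3 | 1 | 1/2 = 0.500 | 1/3 = 0.333 | 0.167 | 0.272 |

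From the first later progression onward, every gap is below one SE. Only between the death and that progression is it marginally larger: for n = 8, 1 − 7/8 = 0.125 against √(0.875 × 0.125/8) = 0.117. A later death affects less of the curve.

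**Step 5. How often this would arise.** If each responder has an assumed chance q of dying before documented progression, the chance of at least one such death is 1 − (1 − q)^n. For 6 to 8 responders this is 26–34% at q = 5%, 47–57% at 10% and 74–83% at 20%.

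**Step 6. Small-sample check.** Trials were simulated with 8 responders, an exponential response duration with a 6-month median, and observation cut at 10 months. With death as an event, the typical Kaplan-Meier median was 5.0 months (with 8 patients the curve reaches 0.5 at the fourth event) and was not reached in 7% of trials. With deaths censored, it was 5.8, 6.8 and 8.0 months for f = 10%, 20% and 30%, and was not reached in 14%, 24% and 35%.

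**Step 7. The descriptive summary.** If only responders with documented progression are averaged, the same simulation gives a mean of about 4.0 months for every f, against a true mean of 6/ln 2 = 8.7 months. That shortfall comes mainly from dropping responders still in response at the cut-off. If a dead responder were instead carried to the end of the year, the mean would rise. Section 8.3.3(a) does not choose, so the direction is not determined.

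**The case against.** The strongest objection is that the upward bias depends on a conflict the documents leave open. The section that sets out the DR analysis, 8.3.3(a), plans no Kaplan-Meier estimate for DR and reserves that method for PFS and OS. Only the sample-size section names it for DR. This stands. A reader might infer that the plan will overstate response duration outright; the documents support that only under 8.2.1.

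A reader might also infer that the plan instructs the analyst to censor deaths. It does not. Censoring is what ordinarily follows when an event definition omits death, but no rule is written.

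Nor will DR and PFS disagree under every definition. The PFS definition in 7.1.1.3 also omits death. The contrast rests on 2.4.2 and 8.3.3(c).

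The size rests on assumptions. The documents support neither the death shares nor the 6-month median, and Step 4 takes the death as the first event. At 0.50 with 8 responders, the level that fixes the median, the gap of 0.071 is well under one SE.

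Finally, a reader might take this as undermining the trial's main result. It does not. DR is one of several secondary endpoints, with no hypothesis or decision rule attached. Neither the response-rate test nor the stage-one rule uses it. The deaths would still appear in OS, in PFS under 2.4.2 and 8.3.3(c), and, if treatment-emergent, in the table of fatal adverse events.

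None of this removes the defect. All three definitions omit death, and neither planned analysis handles a responder who dies without documented progression.

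**Conclusion.** The point holds in conditional form. DR ends only at documented progression or recurrence in all three definitions. Under the Kaplan-Meier analysis in 8.2.1, a responder's death without documented progression would in practice be censored, and DR would be biased upward. Under the descriptive summary in 8.3.3(a), that responder has no DR value and the direction is undetermined.

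The size is illustrative: about 11% or 25% on the median if 10% or 20% of response-ending events are deaths, under constant hazards. In a group of 3 to 8, one early death shifts the later steps of the curve by less than one SE. This is a secondary-endpoint definition that should be corrected, not a threat to the primary conclusion.

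**What to change.** - In 2.4.2, 7.1.1.3 (Duration of overall response) and 8.3.3(a), end DR at documented progression or death from any cause, whichever comes first.
- State that responders alive without progression are censored at their last adequate tumor assessment.
- In 8.3.3(a), replace the mean and SD with the Kaplan-Meier analysis already named in 8.2.1. Adding death alone would leave responders still in response without a value under the descriptive summary.
- In 7.1.1.3, align the PFS definition with 2.4.2 and 8.3.3(c), so that DR and PFS share one event.

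The cost is wording in those sections plus one censoring rule. Death dates are already needed for OS, and for PFS as defined in 2.4.2 and 8.3.3(c), so no new data are required. The reported DR may be slightly shorter.

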### 8.3.4 Other Analyses/Assessments

**Exploratory Analysis:** Understanding the mechanisms of response and resistance to trametinib therapy will be critical to identifying patients who may preferentially benefit the most from this therapy. We propose to investigate this by:

~~Version: data 03-15-2018~~  
~~Protocol GC#: 166521~~  
~~(in optional biopsy specimens) for evidence MAPK pathway activation. IHC will be performed~~  
**(a)** Assess pre-treatment, at time of first scan to assess response, trametinib resistant tumors to assess ERK1/2 phosphorylation. Phosphorylation will be scored in a continuous manner, and difference in phosphorylation between pre-treatment, best response, and post-resistant specimens will be determined by a two-tailed T-test.

**(b)** We will use whole exome and transcriptome deep sequencing (WES; RNAseq) in the pre-treatment, at time of first scan to assess response (optional), and post- progression (optional) tumor biopsy samples to uncover somatic genetic alterations (mutations)

and copy number alterations) and transcriptional events associated with clinical resistance (either de novo or acquired), with a minimum depth of WES coverage of 100X to capture events occurring down to ~10% frequency. We will use tumor microdissection to maximize tumor purity and peripheral leukocytes as normal/germline controls, with appropriate standard correction of the genetic findings for cancer cell fraction. This unbiased analysis is warranted to ensure we capture resistance events that are anticipated (e.g. secondary BRAF or MEK pathway mutations or ERK1/2 upregulation, or HIPPO-YAP pathway upregulation and unexpected and coordinated changes (e.g. genomic amplification + concordant RNA overexpression of a resistance gene). This approach will enable identification and/or validation of RNA signatures of potential resistance events (such as ERK1/2 transcriptional output). The analysis of samples from patients with de novo resistance and of matched paired tumor samples acquired from individual patients before treatment and at acquired resistance will be prioritized for study to facilitate the clinical correlation of the genetic findings with bona fide clinical resistance. For instance, we may find that genetic mutation/amplification or transcriptional upregulation of ERK1/2 is present in tumors from patients with de novo or acquired trametinib resistance. All statistical and genomic analyses will be done with custom scripts and extensively developed pipelines in the R statistical computing framework (████████████████████). Descriptive statistics and graphical methods will be used to analyze the data. Orthogonal validation of specific findings will be done using individualized assays in the clinical specimens (e.g. direct sequencing, SNP arrays, fluorescence in situ hybridization for DNA alterations; q-RT-PCR, IHC for RNA and protein abundance changes) and associated circulating free DNA, where feasible.

(c) When possible, we will generate patient-derived organoids and/or patient-derived xenografts from biopsy specimens from patients that participate in the trial in order to fully interrogate pathways of response and resistance in a highly clinically relevant system. We will use these models to perform pre-clinical trials aimed at overcoming mechanisms of resistance with rationally designed polytherapy.

(d) Circulating cell free DNA (cfDNA) will be assessed for biomarkers of resistance that are identified above. Descriptive statistics and graphical methods will be used to analyze the data.

## 8.4 Evaluation of Safety

Analyses will be performed for all patients having received at least one dose of study drug. The frequencies of individual toxicities thought to be probably, possible, or definitely related to study drug will be reported as well as the incidence of any grade 3, 4, and 5 toxicities regardless of attribution. Analyses will be performed for all patients having received at least one dose of study drug. The study will use the NCI CTCAE v4.03.

## 9 Study Management

### 9.1 Pre-study Documentation

This study will be conducted in accordance with the ethical principles that have their origin in the Declaration of Helsinki as stated in 21 CFR §312.120(c)(4); consistent with GCP and all applicable regulatory requirements.

Before initiating this trial, the Investigator will have written and dated approval from the Institutional Review Board for the protocol, written informed consent form, subject recruitment materials, and any other written information to be provided to subjects before any protocol related procedures are performed on any subjects.

The clinical investigation will not begin until either FDA has determined that the study under the Investigational Drug Application (IND) is allowed to proceed or the Investigator has received a letter from FDA stating that the study is exempt from IND requirements.

The Investigator must comply with the applicable regulations in Title 21 of the Code of Federal Regulations (21 CFR §50, §54, and §312), GCP/ICH guidelines, and all applicable regulatory requirements. The IRB must comply with the regulations in 21 CFR §56 and applicable regulatory requirements.

## **9.2 Institutional Review Board Approval**

The protocol, the proposed informed consent form, and all forms of participant information related to the study (e.g. advertisements used to recruit participants) will be reviewed and approved by the UCSF IRB (UCSF Institutional Review Board). Prior to obtaining IRB approval, the protocol must be approved by the Helen Diller Family Comprehensive Cancer Center Site Committee and by the Protocol Review Committee (PRC). The initial protocol and all protocol amendments must be approved by the IRB prior to implementation.

## **9.3 Informed Consent**

All participants must be provided a consent form describing the study with sufficient information for each participant to make an informed decision regarding their participation. Participants must sign the IRB-approved informed consent form prior to participation in any study specific procedure. The participant must receive a copy of the signed and dated consent document. The original signed copy of the consent document must be retained in the medical record or research file.

## **9.4 Changes in the Protocol**

Once the protocol has been approved by the UCSF IRB, any changes to the protocol must be documented in the form of an amendment. The amendment must be signed by the Investigator and approved by PRC and the IRB prior to implementation.

If it becomes necessary to alter the protocol to eliminate an immediate hazard to patients, an amendment may be implemented prior to IRB approval. In this circumstance, however, the Investigator must then notify the IRB in writing within five (5) working days after implementation. The Study Chair and the UCSF study team will be responsible for updating any participating sites.

## **9.5 Handling and Documentation of Clinical Supplies**

The UCSF Principal Investigator and each participating site will maintain complete records showing the receipt, dispensation, return, or other disposition of all investigational drugs. The date, quantity and batch or code number of the drug, and the identification of patients to whom study drug has been dispensed by patient number and initials will be included. The sponsor-investigator will maintain written records of any disposition of the study drug.

The Principal Investigator shall not make the investigational drug available to any individuals other than to qualified study patients. Furthermore, the Principal Investigator will not allow the investigational drug to be used in any manner other than that specified in this protocol.

